Those who indicate they are interested in participating in research during screening procedures and meet inclusion criteria will be contacted by the PI or a member of the research team (e.g. research coordinator, post-doctoral fellow, or research assistant) to discuss study procedures, answer any questions, and confirm dates/times of appointments. This will occur via telephone, secure zoom video conferencing software, or in-clinic if a member of the research team is available. Participants will then schedule a time to undergo consenting procedures (separate consents for the intervention study and optional psychophysical testing) and a pre-treatment assessment. At the initial visit, the pre-treatment assessment will involve a series of (1) self-report instruments to assess physical and emotional functioning, and (2) in-person psychophysical measures including pain sensory testing and blood draws (optional). Those who use opioids regularly will be instructed to not use opioids prior to their psychophysical testing, as this could impact its outcome. Those who elect to participate in in-person assessment visits will undergo blood draws to assess for potential inflammatory responses to pain. Participants will also provide urine samples for analysis of the presence of infection. Total time in both stages of this assessment will be approximately 90 minutes - approximately 45 minutes to complete patient-reported outcomes and approximately 45 minutes to complete in-person psychophysical assessments.

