- Do you have a stable internet connection/access at home? (circle YES or NO, proceed regardless of answer)

If unsure about any of the above...I may need to ask some additional questions based on your responses today to see if you qualify for the study. Would it be possible for me to call you back with more information (note: contact PI to clarify as needed)?

If no to all of the above, proceed with questions regarding current symptoms: I'd like to ask you a few questions about your current symptoms:

[RESEARCH PERSONNEL MOVE TO RICE CRITERIA AND ASK QUESTIONS]

If qualified via RICE Questionnaire..... then it appears that you qualify to be in the study. Are you interested in taking part in this study?

- No. Thank you for your time.
- Yes. Great. Ask internet question:

Do you have a stable internet connection/access at home? (circle YES or NO, proceed regardless of answer; enrollment might be delayed if NO due to COVID-19, but they will be provided with more information in the future)

If patient does not have a stable internet connection: please inform the participant that due to COVID visitation restrictions we are conducting visits online and that potential study participation will need to be delayed. If this changes in the future we will contact the participant at that time.

Finally, provide available times for intake appointment and schedule with participant.

Note for individuals who are currently taking opiates: Please note that as [REDACTED] study evaluates how [REDACTED] body responds to pain, it is important to not take any medicines the day of the assessment that could change how [REDACTED] may or may not feel pain. If [REDACTED] are taking opiates, [REDACTED] ask that you do not take them before the assessment appointment. [REDACTED] will remind you about this closer to the date as well.

[REDACTED] are very much looking forward to meeting you and having you be a part of this project. Can you please provide me with the best number to reach you and an email address? To make things easier, we would like to remind you of your appointment in a way that best suits you. Can [REDACTED] please let us know if you would prefer a call or a text message?

IN-PERSON SCRIPT

Note to screening provider: prior to contacting a participant, please have a ‘screening form’ ready to fill out in corroboration with the individual’s responses to screening questions.

Hello [name].

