My name is _____ and I work at Vanderbilt University Medical Center. We are conducting a new trial for Interstitial Cystitis/Bladder Pain Syndrome (IC/BPS) and would like to see if you are interested in participating.

The purpose of this discussion is to first tell you more about the study to see if you are interested in participating. I will ask you a brief set of questions about your current symptoms and medical experiences. If you are interested, I can then ask some questions to see if you are eligible to participate in the study. If you would like to proceed with our conversation, it will take approximately ten minutes. This discussion is strictly voluntary. Would you like to continue?

- If YES, proceed
- If NO, thank them for their time and end the conversation

This study is a clinical trial specifically for Interstitial Cystitis (IC). The purpose of this research study is to examine treatments for interstitial cystitis and to learn about different presentations of the condition. Participation involves three assessment visits, and either 8 additional weekly visits that will occur in person, online or over the phone.

The assessment visits would occur in two parts, with the second being optional. Part 1 of the assessment would involve completing a series of questionnaires online. Part 2 would occur in-person and involve providing blood and urine samples, and undergoing testing that evaluates how your body assesses and responds to pain.

The weekly visits will either consist of speaking with a provider via telephone to monitor and discuss your symptom patterns week-by-week or to meet in person or online with a provider to enhance self-management of IC. We will provide compensation for the assessment visits and for travel expenses in some cases.

Do you think you may be interested in taking part in this research study?

- **No.** Thank them for their time and end phone call.
- **Yes,** continue.

Great. I would like to ask you some questions to see if you will be eligible for the study.

Can you please tell me your current age (if over 18, continue)?

Have you been diagnosed with Interstitial Cystitis/Bladder Pain Syndrome (IC/BPS)?

If not, then it does not appear that you qualify for the study. (Thank them for their time and end call) Note: if participant states they suspect they have interstitial cystitis but have not been formally diagnosed, continue and ask RICE screening questions.

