If no to all of the above, proceed with questions regarding current symptoms: I'd like to ask you a few questions about your current symptoms:

[RESEARCH PERSONNEL MOVE TO RICE CRITERIA ON SCORING FORM AND ASK QUESTIONS]

If qualified via RICE Questionnaire..... then it appears that you qualify to be in the study. Are you interested in taking part in this study?

- No. Thank you for your time.
- Yes. Great. Ask internet question:

Do you have a stable internet connection/access at home? (circle YES or NO, proceed regardless of answer; enrollment might be delayed if NO due to COVID-19, but they will be provided with more information in the future)

If patient does not have a stable internet connection: please inform the participant that due to COVID visitation restrictions we are conducting visits online and that potential study participation will need to be delayed. If this changes in the future we will contact the participant at that time.

Finally, provide available times for intake appointment and schedule with participant.

Note for individuals who are currently taking opiates: Please note that as our study evaluates how our body responds to pain, it is important to not take any medicines the day of the assessment that could change how we may or may not feel pain. If you are taking opiates, we ask that you do not take them before the assessment appointment. We will remind you about this closer to the date as well.

We are very much looking forward to meeting you and having you be a part of this project. Can you please provide me with the best number to reach you and an email address? To make things easier, we would like to remind you of your appointment in a way that best suits you. Can you please let us know if you would prefer a call or a text message?

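### The opiate note in both screening scripts is not limited to the optional in-person sensory test, so someone doing only the questionnaires could skip prescribed pain medicine needlessly

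*Combined protocol and SAP*

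**What the plan says.** Section 4.2 states the rule and its reason: "Those who use opioids regularly will be instructed to not use opioids prior to their psychophysical testing, as this could impact its outcome". Sections 4.2, 5.1 and 6.3 make psychophysical testing an optional, in-person stage, and sections 4.2 and 5.1 give it a separate consent. Section 5.3 defines regular use, for stratification, as opioids on more than 3 days per week.

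Both screening scripts end with a note for anyone currently taking opiates. In the in-person script (Appendix C) it gives as its reason that the study looks at the body's response to pain. It then says "it is important to not take any medicines the day of the assessment that could change how we may or may not feel pain", makes the request itself, "If you are taking opiates, we ask that you do not take them before the assessment appointment", and adds "We will remind you about this closer to the date as well". The telephone script (Appendix B) has some words blacked out in the public copy, but the request is still readable: "ask that you do not take them before the assessment appointment".

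Earlier, each script explains what an assessment is: "The assessment visits would occur in two parts, with the second being optional", and "Part 1 of the assessment would involve completing a series of questionnaires online". The last instruction to staff before the note is "Finally, provide available times for intake appointment and schedule with participant".

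**The concern.** Section 4.2 attaches the hold to one procedure that a participant may decline. The scripts attach it to the assessment, a word they have already used for the online questionnaires as well. A listener who plans to do only the questionnaires, and has just been given an intake time, could take the note to apply to that appointment.

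Two things are at stake. The first is participant welfare: a patient with chronic pain may omit prescribed analgesia when nothing in the study needs it. The second, and smaller, is data quality: the GUPI, the primary outcome measure, is among the online questionnaires, so its baseline value could be recorded while opiates are withheld.

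**Working it through.** The plan gives no figure on this point and no arithmetic applies. The check sets the texts side by side.

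1. **The rule and the scripts compared.**

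| | Section 4.2 | Scripts (Appendices B and C) |
|---|---|---|
| Who | Regular opioid users | Anyone currently taking opiates |
| Which medicines | Opioids | Opiates, and other medicines that could change how pain is felt |
| Before what | Psychophysical testing | The assessment, or the assessment appointment |
| Condition on choosing the sensory test | Built in, since the hold is tied to that test | None stated |

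The scripts are wider on every row.

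2. **What the scripts mean by an assessment.** Both present it as two parts, of which Part 1 is online and Part 2 is the optional in-person testing. Nothing in the note narrows the word to Part 2.

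3. **Which appointment the note points to.** It follows the booking of the intake appointment. Under section 5.1 the first contact is a remote visit for consent and online questionnaires, and that section calls it an assessment visit. The same section also uses the term for the first visit to the Clinical Research Center by those who agree to sensory testing. The term therefore covers both visits, and section 5.1 does not settle which one is meant.

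4. **What is known when the note is read.** The separate consent for in-person testing is completed at the enrollment visit (section 5.1), after screening. When the script is read, nobody has consented to the sensory test. The instruction can be right for every listener only if it is conditional on choosing that test.

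5. **Effect on the primary outcome.** If a participant withheld opiates before the online baseline questionnaires, the baseline GUPI would be completed in that state. Section 5.3 places randomization after those questionnaires and stratifies it by opioid use, and section 9.1 adjusts for baseline GUPI. A disturbance that precedes allocation should not favor either arm. The documents do not give the GUPI recall period, so the size of any shift in an individual score cannot be worked out.

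6. **Effect on the sensory data.** Section 9.1 brings one sensory measure into a planned model: baseline temporal summation, one of three exploratory Aim 3 moderators. No sensory test is named there among the secondary outcomes.

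**The case against.** The strongest reply is that the note, read sensibly, already means the sensory test. Its reason closely tracks the script's description of Part 2. Staff book an intake appointment, but the note speaks of an assessment appointment and promises a reminder nearer the date, which fits a second, later visit. Eligible people are also contacted after screening to discuss procedures, and in-person testing has its own consent form. That form is not in the public copy and may say when the hold applies. All of this stands, and it is why the wording is called ambiguous. It does not remove the point, because a reason is not a condition and the request to omit medicine is made without one.

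A reader might infer more than the documents support:

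- *That section 4.2 and the scripts contradict each other on who is covered.* Section 4.2 says regular users will be instructed; it does not say that only they will be. The scripts are broader, and staff reading them have a clear answer. Aligning the two is sensible, but which population to adopt is a matter of preference.
- *That the promised reminder is never given.* The reminder script (Appendix E) has no medication line, but it is a generic template, and section 5.5 provides for other planned contacts by text, call or email. No omission is shown.
- *That the primary comparison is biased, or that GUPI is wholly untouched.* Neither is supported. Baseline GUPI could be affected in some participants, but before allocation.
- *That counting how often the scripts use the word assessment measures the risk.* It shows that the wording is loose, not how many people would act on it.

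**Conclusion.** The point holds as an ambiguity in participant-facing wording with a real, if unquantified, welfare cost. Both scripts ask every current opiate user to withhold opiates, and other medicines that alter pain, without saying that this is only for the optional sensory test. Someone who completes only the questionnaires could follow the request and gain nothing from it.

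The number affected cannot be estimated, since neither opiate use among those screened nor uptake of in-person testing is given. The analytic consequence is limited: baseline GUPI may be recorded off opiates in some participants, with no between-arm bias expected.

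This rests on two assumptions: that the note is read once, at screening, and acted on for the baseline assessment; and that the consent forms, which could not be seen, may or may not clarify it. Even if they do, the scripts should not make an unconditional request that section 4.2 does not make. The change is worth making, but it is not a threat to the primary result.

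**What to change.** In Appendices B and C, add to the opiate note: *This applies only if you choose the in-person sensory test, and only before that test; you do not need to change any medicine for the online questionnaires.*

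Use the same population and the same list of medicines in section 4.2 and in both scripts. Whether that is regular users or all current users who take the sensory test, and whether medicines other than opioids are included, is for the sponsor to decide.

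Two additions are optional: a matching line in the Appendix E reminder for in-person sensory-test visits, and a record of the last analgesic dose and time at each sensory test.

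The cost is re-approval of two scripts, plus an edit to one sentence of section 4.2 if the alignment is made there. Sample size, visits and the primary analysis do not change.

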15. APPENDIX D: INCLUSION/EXCLUSION CHECKLIST

INCLUSION/EXCLUSION CHECKLIST

Inclusion/Exclusion Criteria Checklist

Inclusion criteria (must answer YES):

- 18 years of age or older.
- Diagnosis of IC/BPS as given by providers or indicated by assessments

Exclusion criteria (must answer NO to all):

- Comorbid neurological conditions including spinal cord injury or systematic neurologic illnesses, or central nervous system diseases such as brain tumor or stroke.
- Current or history of diagnosis of primary psychotic or major thought disorder within the past five years;
- Hospitalization for psychiatric reasons other than suicidal ideation, homicidal ideation, and/or PTSD (within the past 5 years);
- Psychiatric or behavioral conditions in which symptoms are unstable or severe (e.g. current delirium, mania, psychosis, suicidal ideation, homicidal ideation, substance abuse dependency) reported within the past six months;
- Non-English speaking
- Presenting symptoms at time of screening that would interfere with participation, specifically active suicidal ideation with intent to harm oneself or active delusional or psychotic thinking;
- Difficulties or limitations communicating over the telephone.
- Any planned life events that would interfere with participating in the key elements of the study.
- Any active major medical issues that would preclude participation.
- Currently being treated for cancer.
- Cancer-related pain.
- Currently engaged in individual counseling/psychotherapy or unwilling to pause this treatment for the trial duration.

16. APPENDIX E: REMINDER SCRIPT

Optimizing Psychosocial Treatment for IC/BPS- Phone/email reminder script

Hello, (insert name here), this is (name) from Vanderbilt University Medical Center. I am contacting you about the Interstitial Cystitis (IC/BPS) treatment study. I would like to remind you that you have an upcoming visit (place) at (time) on (date). I am calling to confirm your appointment and also see if you have any questions about the visit.

If call/text,

(if applicable-)Would you like directions to your visit at the Clinical Research Center/Osher Center for Integrative Medicine?

If YES, provide directions.

Do you have any questions?

If YES, answer questions.

Can you please confirm that you will be at the appointment?

Wonderful, we will see you for your appointment then. Please feel free to call or text me with any questions you may have. If you need to cancel, please let us know in advance as best you can by calling (provide phone number).

Take care!

End call/text.

If email,

[Directions to the Clinical Research Center](#) (plug in your starting point)

Address: [REDACTED], [name]

[Directions to the Osher Center for Integrative Medicine](#) (plug in your starting point)

Address: [REDACTED], [name]

Can you please confirm that you will be at the appointment?

If you need to cancel, please let us know in advance as best you can by calling (provide phone number).

Please feel free to email me with any questions you may have. See you then!

Thank you,
The research team

17. APPENDIX F: RESEARCH MATCH SCRIPT (MEN)

RESEARCH MATCH SCRIPT (MEN)

Are you a male with Interstitial Cystitis/Bladder Pain Syndrome (IC/BPS) interested in participating in a research study?

We are looking for men with Interstitial Cystitis/Bladder Pain Syndrome (IC/BPS) to participate in a clinical trial.

Study purpose: The purpose of this research study is to examine treatments for interstitial cystitis and to learn about different presentations of the condition.

Study duration: Participation involves three assessment visits that can be done completely online if desired, ranging from 45 to 90 minutes each. Also, the study will have 8 additional weekly visits that will occur either in person, online, or over the phone that will be up to 50 minutes each. The assessments and visits will occur over the course of 5 months.

Eligible individuals are adults (18+) with IC/BPS who do not have any of the following: diagnosed neurological conditions including spinal cord injury, brain injury, or stroke, certain psychological conditions including psychotic or bipolar disorder, current severe psychiatric distress, current cancer treatment or cancer-related pain. Participants need to speak English fluently, be able to speak over the phone, have a stable internet connection (if applicable), and be available for eight weekly visits during study participation which may occur in person, online, or by telephone.

Participants will be compensated up to \$300 for their time.

Note: Eligibility will be further determined upon contact and/or completion of the eligibility survey.

18. APPENDIX G: RESEARCH MATCH SCRIPT (WOMEN)

RESEARCH MATCH SCRIPT (WOMEN)

Are you a woman with Interstitial Cystitis/Bladder Pain Syndrome (IC/BPS) interested in participating in a research study?

We are looking for women with Interstitial Cystitis/Bladder Pain Syndrome (IC/BPS) to participate in a clinical trial.

Study purpose: The purpose of this research study is to examine treatments for interstitial cystitis and to learn about different presentations of the condition.

Study duration: Participation involves three assessment visits that can be done completely online if desired, ranging from 45 to 90 minutes each. Also, the study will have 8 additional weekly visits that will occur either in person, online, or over the phone that will be up to 50 minutes each. The assessments and visits will occur over the course of 5 months.

Eligible individuals are adults (18+) with IC/BPS who do not have any of the following: diagnosed neurological conditions including spinal cord injury, brain injury, or stroke, certain psychological conditions including psychotic or bipolar disorder, current severe psychiatric distress, current cancer treatment or cancer-related pain. Participants need to speak English fluently, be able to speak over the phone, have a stable internet connection (if applicable), and be available for eight weekly visits during study participation which may occur in person, online, or by telephone.

Participants will be compensated up to \$300 for their time.

Note: Eligibility will be further determined upon contact and/or completion of the eligibility survey.

19. APPENDIX H: RESEARCH MATCH SCRIPT (GENERAL)

RESEARCH MATCH SCRIPT (GENERAL)

Do you currently have Interstitial Cystitis/Bladder Pain Syndrome (IC/BPS) and are you interested in participating in a research study?

We are looking for individuals with Interstitial Cystitis/Bladder Pain Syndrome (IC/BPS) to participate in a clinical trial.

Study purpose: The purpose of this research study is to examine treatments for interstitial cystitis and to learn about different presentations of the condition.

Study duration: Participation involves three assessment visits that can be done completely online if desired, ranging from 45 to 90 minutes each. Also, the study will have 8 additional weekly visits that will occur either in person, online, or over the phone that will be up to 50 minutes each. The assessments and visits will occur over the course of 5 months.

Eligible individuals are adults (18+) with IC/BPS who do not have any of the following: diagnosed neurological conditions including spinal cord injury, brain injury, or stroke, certain psychological conditions including psychotic or bipolar disorder, current severe psychiatric distress, current cancer treatment or cancer-related pain. Participants need to speak English fluently, be able to speak over the phone, have a stable internet connection (if applicable), and be available for eight weekly visits during study participation which may occur in person, online, or by telephone.

Participants will be compensated up to \$225 for their time.

Note: Eligibility will be further determined upon contact and/or completion of the eligibility survey.

